(PEEP) has been shown to attenuate the derangement of respiratory mechanics and the impairment in oxygenation caused by PP⁽¹⁰⁻¹⁵⁾. In addition, the application of PEEP as a part of intraoperative protective mechanical ventilation may be associated with a decrease in PPCs following laparoscopic surgery⁽¹⁶⁾. Nevertheless, there is no consensus on the optimal PEEP level and the best method to set PEEP during laparoscopic surgery⁽⁹⁾. In patients with acute respiratory distress syndrome (ARDS), Talmor et al⁽¹⁷⁾ demonstrated that mechanical ventilation with PEEP set according to P_{pl} measured by using esophageal balloon catheter significantly had beneficial effects in terms of oxygenation, C_{RS} and possible mortality. With PEEP set according to this method, the transpulmonary pressure (P_{TP}), which is the difference between the pressure inside alveoli or PEEP and the pressure outside or P_{pl} , is constantly maintained positive during expiration. Consequently, it helps to prevent the formation of atelectasis as well as to recruit the collapsed alveoli and, thus, to improve oxygenation. To date, there is limited data regarding the use of esophageal balloon catheter to set PEEP in mechanically ventilated patients undergoing laparoscopic surgery. Therefore, the aim of this study is to determine whether PEEP titration guided by P_{pl} measurement during laparoscopic surgery would improve pulmonary function in term of oxygenation as well as other parameters such as compliance and alveolar dead space.

Material and Method

Patient population

This randomized controlled trial includes patients with age of equal or more than 18 years old undergoing laparoscopic gynecologic surgery with anticipated surgical duration of more than 2 hours. Patients with the American Society of Anesthesiologists (ASA) physical status of equal or more than 3, those with significant cardiovascular or respiratory diseases, those with significant pathological lesion in pharynx and esophagus that preclude placement of esophageal balloon catheter, those with contraindications for PEEP titration such as increased intracranial pressure or unstable hemodynamic, those with arrhythmias, those who refuse to provide written informed consent, and those undergoing surgery with duration of less than 2 hours are excluded from the study. Informed consent is obtained from all included patients.

Study protocol

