The primary endpoint of the study is to determine the difference in oxygenation that is PaO₂ between the Group E and the Group C. Spadaro et al⁽¹⁵⁾ reported PaO₂ of 127.5±30 mm Hg during PP in patients undergoing laparoscopic abdominal surgery with application of PEEP of 5 cm H₂O. Meanwhile, PaO₂ was reported as high as 142.5±30 mm Hg⁽¹⁵⁾ to 190.2±11.9 mm Hg⁽¹²⁾ during PP with application of PEEP of 10 cm H₂O. Given that PaO₂ in the Group C is equal to that reported by Spadaro et al⁽¹⁵⁾ and estimated 20% higher PaO₂ in the Group E is clinically relevant, with a power of 0.8 and a significance level of 0.05, sample size of 22 subjects per group is required. The secondary endpoints are the difference in C_{RS} and V_D/V_T between the two groups, changes in hemodynamic parameters with application of PEEP, proportion of thoracoabdominal transmission of IAP as well as adverse respiratory events and length of hospital stay in the two groups.

Categorical variables are reported as number with percentage and compared between the groups using the chi-squared test or the Fisher's exact test as appropriated.

Continuous variables are tested for normal distribution with the Kolmogorov–Smirnov test and reported as mean with standard variation (SD) or median with interquartile range (IQR) and compared between the groups using the unpaired Student's t-test or the Mann Whitney U test as appropriated. The changes in parameters within the group are analyzed using the repeated-measure analysis of variance (ANOVA). For all analyses, a two-tailed test is performed and a *p* value of less than 0.05 is considered statistical significance. The statistical analysis is carried out using the IBM SPSS Statistics 21 (IBM Corporation, New York, USA).

Reference

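### The 22 per group leaves no margin: t-test power is 0.786 if all 22 are analysed, and lower with any unreplaced exclusion for surgery under 2 hours

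*Combined protocol and SAP*

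**What the plan says.** The Statistical analysis section defines the primary endpoint: "The primary endpoint of the study is to determine the difference in oxygenation that is PaO₂ between the Group E and the Group C". For Group C it takes a published value, "PaO₂ of 127.5±30 mm Hg during PP in patients undergoing laparoscopic abdominal surgery with application of PEEP of 5 cm H₂O". For Group E it sets the target as an "estimated 20% higher PaO₂ in the Group E is clinically relevant". It then concludes that "with a power of 0.8 and a significance level of 0.05, sample size of 22 subjects per group is required". The formula is not named.

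The same section says "For all analyses, a two-tailed test is performed" and compares continuous variables by the unpaired "t-test or the Mann Whitney U test as appropriated".

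The Patient population section admits patients on the expected length of surgery (over 2 hours). It then adds, among the exclusions, that "those undergoing surgery with duration of less than 2 hours are excluded from the study". Under Data collection, PEEP is set by allocated group once pneumoperitoneum and the Trendelenburg position are established. T1 is recorded 15 minutes later and T2 one hour later.

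The text seen contains no allowance for losses, no rule for replacing excluded patients, and no statement of whether 22 means randomised or analysed.

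**The concern.** Two features act together.

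First, 22 is what the normal formula gives. The t-test estimates the SD from the data and needs slightly more patients, so at 22 per group there is nothing in hand.

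Second, the duration exclusion appears to operate after allocation. Entry already depends on anticipated duration, so a second rule on duration adds something only if it refers to actual duration. That is known only when surgery ends, after the patient has been ventilated according to group. Unless such patients are replaced, each one reduces the number analysed.

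The sentence on sample size gives the only power figure in the plan. A non-significant PaO₂ difference would be read against 0.80, while the power actually available could be 0.70 to 0.77 after a few exclusions per group.

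**Working it through.** **Inputs (Statistical analysis section)**
- Control mean 127.5 mm Hg, SD 30.
- Difference 0.20 × 127.5 = 25.5 mm Hg, so the Group E mean is 153.0.
- Two-sided alpha 0.05, target power 0.80, equal groups.
- Assumption: a common SD of 30 in both groups. The plan does not state the Group E SD for the calculation, but quotes 30 in one of its two sources at PEEP 10 cm H₂O.

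Standardised difference: 25.5 / 30 = 0.85.

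**1. Reproducing the plan's figure.** Normal approximation:

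n = 2 × (1.960 + 0.842)² / 0.85² = 21.73, rounded up to 22 per group.

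This matches. The same approximation gives power 0.805 at 22. A one-sided calculation would give 18, so the two-sided formula was evidently used.

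**2. Power of the named test.** For a two-sided t-test with n analysed per group, the degrees of freedom are 2n − 2 and the noncentrality is 0.85 × √(n/2). At n = 22 the noncentrality is 0.85 × √11 = 2.819, with 42 degrees of freedom and critical value 2.018. Power is 0.786. Solving for power 0.80 gives n = 22.73, so 23 per group.

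**3. Power by number analysed.** The documents give no loss rate, so the rows below 22 are an assumed range.

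| Analysed per group | Lost from 22 | t-test power |
|---|---|---|
| 23 | – | 0.805 |
| 22 | 0 | 0.786 |
| 21 | 1 (5%) | 0.767 |
| 20 | 2 (9%) | 0.745 |
| 19 | 3 (14%) | 0.722 |
| 18 | 4 (18%) | 0.698 |

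The difference detectable with power 0.80 is 25.9 mm Hg (20.3% of 127.5) at 22 per group and 27.3 mm Hg (21.4%) at 20.

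**4. Adjusting for T0 PaO₂.** If the correlation between T0 and outcome PaO₂ is ρ, the residual SD is 30 × √(1 − ρ²): 28.6 for ρ = 0.3 and 26.0 for ρ = 0.5. The degrees of freedom are 2n − 3. The documents give no correlation, so both values are assumed. In each range, the lower figure allows for chance baseline imbalance and the upper does not.

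| Analysed per group | ρ = 0.3 | ρ = 0.5 |
|---|---|---|
| 22 | 0.81–0.82 | 0.88–0.89 |
| 20 | 0.77–0.78 | 0.85–0.86 |

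**The case against.** **The stated figure is not wrong.** The plan's inputs give 22 by a standard formula, and the plan names no other. The t-test shortfall is 1.4 percentage points, or one patient per group, and 0.786 still rounds to 0.8. An SD of 29.5 instead of 30 would close it, and planning SDs are not known that precisely. All of this stands. A reader might infer that the sample size is an arithmetic error, or that the design fails its stated power even when complete. The documents do not support either reading.

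**The losses are not established.** The plan says 22 are required. It does not say that recruitment stops at 44 or that excluded patients are not replaced. If 22 means analysed patients, exclusions cost no power. Selecting on anticipated duration should also keep short operations uncommon. These points stand as well, so the lower powers are conditional and no particular loss rate can be attributed to the plan. They do not remove the ambiguity: the text gives neither a replacement rule nor a definition of the 22. Part of the document after the reference list was not seen, but the Statistical analysis section runs complete up to that list.

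**The rank test.** A reader might infer a further loss of power if Mann-Whitney is used. The usual relative efficiency of 0.955 holds under normality, whereas the plan would turn to that test mainly when normality is rejected. No power figure for that case can be derived from the documents.

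**The remedy is partial.** At an assumed correlation of 0.3, adjustment does not fully restore 0.80 with 20 per group. That is correct.

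**Conclusion.** The concern holds in a limited form. The 22 per group is a correct normal-approximation result with no reserve: the planned t-test has power 0.786 if all 22 are analysed. The duration exclusion, read as actual duration, falls after allocation, and no loss allowance or replacement rule was found. Any unreplaced exclusion therefore takes power clearly below 0.80, to 0.767 with one lost per group and 0.698 with four.

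This rests on a difference of 25.5 mm Hg, a common SD of 30, equal numbers analysed per group, and no replacement of excluded patients. The no-loss gap alone would not justify a change. The missing margin combined with a built-in exclusion does, because the correction is cheap.

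**What to change.** 1. Restate the power by number analysed, for example: *22 analysed patients per group give power about 0.79 (two-sided t-test) for 153.0 versus 127.5 mm Hg, SD 30, falling to about 0.75 if 20 per group are analysed.* Next to it, say whether 22 counts randomised or analysed patients and whether those excluded for short surgery are replaced.
2. Make the primary PaO₂ comparison an analysis of covariance adjusted for T0 PaO₂, specified in advance. Data collection already provides T0. State any power quoted for it with its assumed correlation.

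The cost is a slightly less favourable stated power and a pre-specified covariate in the primary analysis, which is a change of method and not only of wording. No extra patients or measurements are needed.

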For management of mechanical ventilation, all patients are ventilated by an anesthetic machine (Aespire View, Datex-Ohmeda Inc., Wisconsin, USA) with preset tidal volume of 8 mL/kg of predicted body weight, inspiratory to expiratory time ratio of 1:2 with 45% inspiratory pause, respiratory rate adjusted to maintain end-tidal carbon dioxide (EtCO₂) between 35 and 45 mm Hg, fraction of inspired oxygen (FiO₂) of 0.40 in one liter per minute of the mixture of oxygen and air which can be adjusted to maintain peripheral oxygen saturation (SpO₂) of equal or more than 95% and PEEP set according to the study groups. All included patients are randomly allocated into 2 groups, the control group (Group C) and the intervention group (Group E), by computer-generated block-of-four randomization. In the Group E, the 5-French, latex-free adult esophageal balloon catheter (CooperSurgical Inc., Connecticut, USA) is inserted after induction and intubation and connected to the pressure transducer system (TruWave, Edwards

Lifesciences, Irvine, USA). The proper position of the catheter is in the lower one third of the esophagus, which is determined by rising in pressure during positive pressure ventilation plus presence of cardiac oscillation recognized on the pressure tracing⁽¹⁸⁻²⁰⁾. The esophageal pressure (P_{eso}) is measured and used as a surrogate of P_{pl} ⁽¹⁹⁻²¹⁾. PEEP is titrated to maintain P_{TP} during expiration, which is equal to PEEP minus P_{eso} during expiration, between 0 and 5 cm H₂O. The conversion factor of 1.36 is used to convert mm Hg to cm H₂O. In the group C, the esophageal balloon catheter is inserted as in the group E for measuring P_{eso} but patients are ventilated with fixed PEEP of 5 cm H₂O throughout the operation.

Data collection

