In all patients, demographic data including age, weight, height, body mass index (BMI), the ASA physical status, comorbid diseases, diagnosis, operation, duration of the operation are recorded. After induction and intubation and insertion of the esophageal balloon catheter, hemodynamic parameters including blood pressure, heart rate, cardiac index and stroke volume index; respiratory mechanics including peak inspiratory pressure, plateau pressure (P_{plat}), PEEP, P_{eso} during inspiration and expiration, and tidal volume; and gas exchange parameters including partial pressure of arterial oxygen (PaO₂) and carbon dioxide (PaCO₂), pH, FiO₂, SpO₂ and EtCO₂ are recorded as baseline T0 parameters. After initiation of PP and position in 45-degree Trendelenburg position, PEEP is set according to patient's group allocation. Hemodynamic parameters, respiratory mechanics, gas exchange parameters and IAP are recorded at 15 minutes and at one hour after setting of PEEP as T1 and T2 parameters, respectively. Thirty minutes after arrival in the recovery room, hemodynamic and gas exchange parameters are

recorded again as T3 parameters. The C_{RS} is calculated from tidal volume in mL divided by difference between P_{plat} and PEEP in cm H₂O and the alveolar dead space to tidal volume ratio (V_D/V_T) is calculated using the formula reported by Hardman et al⁽²²⁾. Adverse respiratory events defined as requirement of oxygen supplement after discharge from the recovery room, episodes of desaturation (SpO₂ of less than 90%), new-onset respiratory infection, new infiltration on chest radiograph, or respiratory failure are followed up in all patients for 72 hours postoperatively or until discharge from hospital. Length of hospital stay as well as other adverse events are also recorded.

Statistical analysis

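### The between-group comparison of PaO₂ ignores the T0 PaO₂ recorded in every patient: valid, but less precise than baseline adjustment if T0 correlates with the outcome above about 0.16

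*Combined protocol and SAP*

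**What the plan says.** Under Data collection, hemodynamic, respiratory-mechanics and gas-exchange values, PaO₂ among them, are taken after induction, intubation and balloon insertion and "are recorded as baseline T0 parameters". The next step is described so: "After initiation of PP and position in 45-degree Trendelenburg position, PEEP is set according to" the allocated group. PaO₂ is then measured at T1 (15 minutes after PEEP setting), T2 (one hour) and T3 (30 minutes after arrival in recovery).

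Under Statistical analysis, "The primary endpoint of the study is to determine the difference in oxygenation", specified as PaO₂ in Group E against Group C. No time point is attached. Continuous variables are checked with a Kolmogorov–Smirnov test and then compared between groups by the unpaired "t-test or the Mann Whitney U test as appropriated". Repeated values are used as follows: "The changes in parameters within the group are analyzed using the repeated-measure analysis of variance". That analysis describes each group over time and does not compare the groups. No ANCOVA, change score or other baseline adjustment is specified for the PaO₂ comparison.

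Two statements on ventilation in the Study protocol section bear on whether T0 can be used. In Group C, "patients are ventilated with fixed PEEP of 5 cm H₂O throughout the operation". The inspired oxygen fraction starts at 0.40, "which can be adjusted to maintain peripheral oxygen saturation".

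**The concern.** The trial measures its own primary variable before the allocated PEEP is set (on the Data collection account) and then leaves that measurement out of the primary comparison. With 22 patients per group, chance differences at T0 are not small. If T0 PaO₂ also has SD 30 mm Hg (an assumption), the between-group difference at T0 has a standard error of 30 × √(2/22) = 9.0 mm Hg, more than a third of the 25.5 mm Hg the trial is designed to detect. If T0 and the outcome have equal SDs and correlate at 0.5, about half of any such imbalance carries into the unadjusted estimate. Randomisation makes this average to zero over repeated trials, but in any one trial it is noise that a covariate could remove. Without a prespecified model, a visible T0 imbalance would also invite a choice of adjustment after the data are seen.

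**Working it through.** **Inputs (Statistical analysis section).** Control mean 127.5 and SD 30 mm Hg; target 20% higher, so Δ = 0.20 × 127.5 = 25.5 mm Hg and Δ/SD = 0.85; two-sided 0.05; power 0.80; n = 22 per group, N = 44. **Assumed:** the correlation r between T0 and outcome PaO₂, which the documents do not give; a roughly linear relation; SD 30 in both groups.

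**1. The plan's own figure.** The plan states "with a power of 0.8 and a significance level of 0.05, sample size of 22 subjects per group is required". By the normal approximation, n = 2 × [30 × (1.960 + 0.842)/25.5]² = 21.73, rounded up to 22. The figure reproduces.

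**2. The planned t-test.** Noncentrality = 0.85 × √(22/2) = 2.82 on 42 df. Power is 0.786 (0.805 with 23 per group). The 95% CI half-width is about 2.018 × 30 × √(2/22) = 18.3 mm Hg.

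**3. ANCOVA on T0.** Relative to the t-test, the variance of the adjusted difference is

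(1 − r²) × [1 + 1/(N − 4)] = (1 − r²) × 1.025.

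The second factor is the price of estimating the slope. Noncentrality is 2.82 divided by the square root of this ratio, on 41 df. At r = 0.5, for example, the ratio is 0.75 × 1.025 = 0.769.

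| r (assumed) | Variance ratio | Half-width, mm Hg | Power |
|---|---|---|---|
| t-test | 1 | 18.3 | 0.786 |
| 0 | 1.025 | 18.5 | 0.776 |
| 0.2 | 0.984 | 18.1 | 0.792 |
| 0.3 | 0.933 | 17.6 | 0.813 |
| 0.5 | 0.769 | 16.0 | 0.881 |
| 0.7 | 0.523 | 13.2 | 0.968 |

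**4. Break-even.** Setting (1 − r²) × 1.025 = 1 gives r = √(1/41) = 0.156. The break-even is 0.161 on CI width and 0.159 on power; all three round to 0.16. Power reaches 0.80 at r = 0.24. At r = 0.5 the gain equals a t-test with about 28 per group.

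**5. Check by simulation.** With 200,000 trials per setting, the variance ratios were 1.025, 0.984, 0.768 and 0.523 at r = 0, 0.2, 0.5 and 0.7, in line with the formula. Type I error was 0.049 to 0.051 for both the t-test and ANCOVA.

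**6. The Mann-Whitney branch.** On normal data its power is about 0.77 (0.767 from relative efficiency 0.955; 0.766 by simulation). The 0.16 threshold is for ANCOVA against the t-test and does not carry over exactly to this test.

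**7. Is T0 free of allocation?** Data collection puts the group PEEP setting after T0, following pneumoperitoneum and positioning. The Study protocol section fixes Group C's PEEP for the whole operation and states no PEEP for Group E at T0. On the first reading T0 precedes the intervention; on the second it might not. The documents do not settle this.

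**The case against.** The strongest reply is that the plan contains no error here. The planned test is valid, the sample size was computed for that test, and the two agree. The benefit of adjustment rests on a correlation the documents do not supply, and there are reasons it could be weak: T0 precedes pneumoperitoneum and the 45-degree Trendelenburg position, and inspired oxygen may be changed afterwards. Just above 0.16 the gain is trivial: at 0.2, power rises by 0.6 of a point. The shortfall from 0.80 to 0.786 is a matter of normal approximation against exact t, and one more patient per group would close it. The SD of 30 is itself a choice. The plan also cites an SD of 11.9 at PEEP 10; taking 30 in Group C and 11.9 in Group E, unadjusted power is about 0.95 and ANCOVA at r = 0.5 gives about 0.985. The plan's general wording on continuous variables could be read to allow comparison of change scores. And if T0 turned out to depend on allocation, the remedy would be unavailable.

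Much of this stands, and it makes the point a recommendation rather than a correction. It does not remove it. The downside is known and small, the possible gain is substantial, and the measurement is already being taken. A change score is neither specified for PaO₂ nor an equivalent substitute: with equal variances it beats the unadjusted comparison only if r exceeds 0.5. The dependence on T0 being free of allocation is a condition on the fix, and the contradiction needs resolving in any case.

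**Conclusion.** The concern holds as a missed gain in precision. The PaO₂ comparison is valid as planned, but it leaves out a baseline value that would sharpen it if T0 and outcome correlate above about 0.16. The gain is negligible near that threshold and material at moderate correlation: at 0.5, power rises from 0.786 to 0.881 and the CI half-width falls from 18.3 to 16.0 mm Hg. If the correlation is zero, the loss is about one point of power and a CI about 1% wider. These figures assume a common SD of 30 mm Hg, a linear relation, 22 analysed per group, and a T0 value that allocation cannot have affected. The change should be made; confidence that it will pay off is moderate, because the correlation is unknown.

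**What to change.** 1. Reconcile the Study protocol and Data collection sections on when group-specific PEEP begins. If T0 could be affected by allocation, do not use it as a covariate.
2. Name one primary time point. The sample-size figures are for PaO₂ during pneumoperitoneum, which points to T1 or T2 rather than T3.
3. Prespecify ANCOVA of PaO₂ at that time on group and T0 PaO₂, reporting the adjusted difference with its 95% CI. Keep the unadjusted difference as a supporting analysis.
4. With the model fixed in advance, the normality pretest no longer selects the primary test and can be dropped for that endpoint. Keep a rank-based analysis as sensitivity.
5. Report inspired oxygen fraction by group at T0 and at the primary time point, so that readers can judge PaO₂ against it.
6. Use the same model for secondary continuous measures with a T0 value (C_RS, V_D/V_T, hemodynamics). For hemodynamics, which the plan words as changes, modelling the change with T0 as covariate gives the same group effect. It does not apply to length of stay, or to transmission of intra-abdominal pressure, since that pressure is listed only at T1 and T2.

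The cost is SAP wording, one named time point and one clarification of the protocol. No new data are needed. The statistical price is one degree of freedom and an estimated slope.

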Prior to induction of general anesthesia, standard monitoring including non-invasive blood pressure measurement, pulse oxymetry, electrocardiogram, capnometry and peripheral nerve stimulator (TOF-Watch, Organon, Ireland), which is applied to the temporal branch of facial nerve and recorded response of the orbicularis oculi, as well as non-invasive cardiac output measurement with the pulse wave transit time technology (Vismo, Nihon Kohden, Japan) are applied to all patients. General anesthesia is induced with 1.5-2 mg/kg of propofol, 2 mcg/kg of fentanyl and 0.6 mg/kg of rocuronium and then trachea is intubated with proper size of endotracheal cuff tube. After induction and intubation, arterial catheter is inserted at radial artery for repeated arterial blood gas sampling. Anesthesia is maintained with 1 minimal alveolar concentration (MAC) of

desflurane and supplemental doses of morphine and rocuronium as required. Train-of-four (TOF) stimulation with peripheral nerve stimulator is kept between 1 and 2 twitches to facilitate relaxation. In case of hemodynamic instability, fluid as well as inotropes and vasopressors are administered according to discretion of anesthesia staff. The surgery is initially started in the lithotomy position and then in the 45-degree Trendelenburg position at the initiation of PP. PP is created by intraabdominal insufflation of carbon dioxide (CO₂) and IAP is maintained at 12 to 15 mm Hg during PP. At the end of the surgery, reversal of paralysis with 0.2 mg of sugammadex is administered and extubation is carried out after fulfilled criteria of extubation and TOF ratio monitoring of more than 90%. All patients are then transferred to the recovery room and monitored for 1.5 hours prior to transfer to ward.

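### The within-group ANOVA cannot isolate the hemodynamic effect of setting PEEP; the randomised comparison can, but the plan does not link it to that endpoint

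*Combined protocol and SAP*

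**What the plan says.** **Endpoint.** In the Statistical analysis section of the combined protocol and SAP, the secondary endpoints include "changes in hemodynamic parameters with application of PEEP, proportion of thoracoabdominal transmission of IAP as well as adverse respiratory events".

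**Methods.** The same section has two general sentences on continuous data. One compares the groups by the unpaired "t-test or the Mann Whitney U test as appropriated". The other covers change over time: "The changes in parameters within the group are analyzed using the repeated-measure analysis of variance (ANOVA"). Neither names an endpoint or a time point, and neither mentions adjustment for baseline.

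**Timing.** Under Data collection, T0 is read after induction, intubation and insertion of the esophageal catheter. Then: "After initiation of PP and position in 45-degree Trendelenburg position, PEEP is set according to" the allocated group. The next readings come after that: "IAP are recorded at 15 minutes and at one hour after setting of PEEP as T1 and T2 parameters". The last is T3: "Thirty minutes after arrival in the recovery room, hemodynamic and gas exchange parameters are" taken once more. The Study protocol section has patients start in lithotomy and "then in the 45-degree Trendelenburg position at the initiation of PP", with extubation at the end of surgery. It also leaves fluid, inotropes and vasopressors to the anesthesia staff when hemodynamics are unstable, and allows supplemental morphine and rocuronium.

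**The concern.** The endpoint asks what applying PEEP does to hemodynamics. The one method named for changes compares a patient's later readings with earlier ones, and between T0 and T1 three things happen with no reading in between: insufflation, steep head-down tilt and the PEEP setting. A significant time effect within a group would show that something changed, but not that PEEP changed it.

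Two misreadings are at stake. A significant ANOVA could be reported as a PEEP effect when it reflects pneumoperitoneum and tilt. And if one group reached significance and the other did not, that could be reported as a difference between PEEP strategies although no test had compared them. Meanwhile the comparison that does isolate the PEEP strategy, Group E against Group C during pneumoperitoneum, would have no stated role for this endpoint.

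**Working it through.** **1. Group size.** The plan's only sample-size figure is for PaO₂: control mean 127.5, SD 30, difference 20% × 127.5 = 25.5 mm Hg, power 0.8, two-sided 0.05. Normal approximation: n = 2 × [(1.960 + 0.842) × 30 / 25.5]² = 21.7, so 22 per group. This reproduces, and 22 is used below.

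**2. What each within-group pair contains.** Four hemodynamic readings give 4 × 3 / 2 = 6 pairs.

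| Pair | What lies between the readings |
|---|---|
| T0–T1 | pneumoperitoneum, tilt, PEEP setting |
| T0–T2 | the same, plus 45 minutes |
| T0–T3 | all of these, plus end of surgery and extubation |
| T1–T2 | time only; both follow the PEEP setting |
| T1–T3 | end of surgery, extubation |
| T2–T3 | end of surgery, extubation |

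Pairs that isolate the PEEP setting: 0 of 6. If Group C's PEEP is constant for the whole operation, as the Study protocol section says, its T0–T1 change contains no PEEP step at all, yet the ANOVA would test it.

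**3. How often the ANOVA is significant with no PEEP effect.** Simulation with 22 per group, four readings with equal correlation, and the same mean shift at T1 and T2 in both groups. The shift stands for pneumoperitoneum and tilt. Shift and correlation are assumptions; the documents give neither.

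| Assumed correlation | Shift 0.25 SD | Shift 0.5 SD | Shift 0.8 SD |
|---|---|---|---|
| 0.3 | 17% | 62% | 97% |
| 0.5 | 24% | 77% | 99.5% |
| 0.7 | 39% | 95% | 100% |

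These are the proportions of trials with p < 0.05 within one group. Although the two groups are identical by construction, one is significant and the other not in up to 48% of trials (correlation 0.3, shift 0.5 SD). The between-group t-test at T1 rejects in 4.3–5.7% throughout, because a shift common to both groups cancels.

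**4. Precision of the between-group comparison.** Detectable difference at 80% power, two-sided 0.05, 22 per group, noncentral t. It is about 0.865 × residual SD (0.8652 with 41 degrees of freedom), in units of the SD at one time point. Here r is the correlation of T0 with T1 and with T2 (taken as equal), and r12 is the correlation of T1 with T2.

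- Unadjusted, one time point: residual SD 1, giving **0.865 SD**.
- T0-adjusted, one time point: residual SD = √(1 − r²). r = 0.5: 0.8652 × 0.8660 = **0.749**. r = 0.7: 0.8652 × 0.7141 = **0.618**.
- T0-adjusted mean of T1 and T2: residual SD = √[(1 + r12)/2 − r²], with r12 = 0.8. r = 0.5: 0.8652 × √(0.90 − 0.25) = **0.698**. r = 0.7: 0.8652 × √(0.90 − 0.49) = **0.554**.

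With r from 0.3 to 0.7 and r12 from 0.7 to 0.9 the last range widens to 0.80–0.52 SD. Averaging alone, without T0, gives about 0.82 SD at r12 = 0.8, so part of the gain is not due to T0. With r = 0 and r12 = 1 there is no gain.

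**The case against.** The strongest reply is that the plan already contains a valid test. Hemodynamic variables are continuous, the plan compares continuous variables between the groups, and the secondary-endpoint sentence ends by referring to the two groups. The ANOVA sentence is general and does not name hemodynamics. All of this stands. A reader might infer that the plan assigns a wrong test to this endpoint, or has no valid one; the documents do not support either. What remains is that the only sentence about changes points to an analysis that cannot answer an endpoint worded as changes, and that the valid test has no stated link to it and no time point.

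A reader might also infer that leaving out T0 biases the comparison. It does not: under randomisation it costs precision only. The absence of T0 is itself read from silence, since the unpaired test could be run on changes from T0.

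It is also fair to say that the detectable differences measure the benefit of the remedy, not the defect, that they rest on assumed correlations, and that averaging T1 and T2 changes the quantity estimated. The defect itself is shown by the count of pairs, which needs no assumption, and illustrated by the simulation, which does.

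**Conclusion.** The point holds for one secondary endpoint. No within-group pair of readings isolates the PEEP setting (0 of 6), so the within-group ANOVA cannot show the hemodynamic effect of applying PEEP. With no PEEP effect it would be significant in about 24% to 99.5% of trials for assumed shifts of 0.25–0.8 SD at correlation 0.5, against about 5% for the between-group test. The size depends on those assumptions; the failure to isolate PEEP does not. The between-group contrast answers a specific question, guided versus fixed PEEP, and not PEEP versus none.

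Two side matters need clarifying but do not carry the point.

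- **IAP transmission.** The text gives no formula for the proportion of intraabdominal pressure transmitted to the chest. IAP is listed only at T1 and T2, so dividing a change in esophageal pressure by absolute IAP assumes a negligible IAP at T0. A change from T0 may also include transmitted PEEP. A reader might infer that the result must be contaminated; the documents do not allow that contribution to be sized, and it may be zero.
- **PEEP at T0.** It is not stated for Group E. The Study protocol section has Group C's PEEP fixed for the whole operation, while Data collection sets PEEP by allocation only after pneumoperitoneum and tilt. For Group C the two can be read consistently, so it would be too strong to call both groups undefined. The T0 list does record "plateau pressure (P_{plat}), PEEP, P_{eso} during inspiration and expiration, and tidal volume", so the actual level will be known.

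The primary PaO₂ comparison and the 22 per group are unaffected.

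**What to change.** 1. **Name the inferential analysis.** For each hemodynamic variable, compare the groups over T1–T2 in a repeated-measures mixed model with group, time, group × time and the T0 value. Report the group difference averaged over T1–T2 with its 95% CI, as the effect of guided versus fixed PEEP.
2. **Make within-group changes descriptive.** Label them as the combined effect of pneumoperitoneum, tilt, any PEEP step, elapsed time, and discretionary fluid, inotropes, vasopressors and supplemental drugs. Describe T3 separately.
3. **Define IAP transmission.** State the formula, units, time point and group. Say that T0 IAP is taken as negligible if absolute IAP is the divisor, and that a change in esophageal pressure from T0 may include transmitted PEEP.
4. **Reconcile** the Study protocol and Data collection sections on PEEP at T0, including Group E.

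Cost: wording only. The hemodynamic readings at T0, T1 and T2 are already collected, no new reading is needed, and the sample size does not change. The change should be made before the data are analysed.
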